19. Frank LL. Thiamine in clinical practice. *JPEN J Parenter Enteral Nutr* (2015) 39(5):503–20. doi:10.1177/0148607114565245 10

PART –E

BUDGET

I. Total Budget: 2,50,000 bdt (Two lacs and fifty thousand taka only)

II. Detailed Budget:

1. Personnel cost: Not Applicable.
2. Field Expenses/ Laboratory Costs: 1,50,000.
3. Supplies and Materials:
4. Patient Cost (if applicable): Transport fee 55,000.
5. Travel cost (Internal travel cost only) : 5000.
6. Transportation of Goods: Not Applicable.
7. Office Stationary: Internet 5000
 Stationary 5000
 Photocopy 5000.
8. Data Processing/ Computer Charges: 15,000.
9. Printing and Reproduction: 10,000.
10. Contractual Services (other than manpower): Not Applicable.
11. Administrative Overhead: Not Applicable.
12. Miscellaneous: Not Applicable.

PART-G

CASE RECORD FORM

Title: Efficacy of Thiamine in Patients with Clinically Suspected Dry Beriberi: An Open Labeled Hospital Based Study.

ID no: **Ward No:** **Bed no:** **Reg. No:**

Date of admission: **Date of Discharge:**

Date of inclusion in study:

Contact No: **Address:**

Particulars of the Patient:

1. Name:
2. Age (in years):
3. Sex: Male=1/Female=2.
4. Religion: Muslim=1/ Hindu=2/Buddist=3 / Christian=3
5. Marital Status: Married=1/ Unmarried=2/ widow=3/divorced=4.
6. Residence: urban=1/ semi urban=2/rural=3/others=4(specify).
7. Education:
8. Occupation:
9. Monthly Income:
10. Food Habit:
 - a) Rice eaten: Polished un-boiled=1/polished boiled=2
 - b) Washing before cooking:times
 - c) Discarding excess water after cooking: no=1/yes=2.
 - d) No of meals per day:

e) Contents of major meals:

Breakfast	Snacks	Lunch	Afternoon Snacks	Dinner

f) Anti-thiamine food intake: Betel nut/ tea/ fermented fish/shell fish.

.....min after major meal,.....times per day

11. Alcohol intake:

Duration.....years, Amount:...../day

current alcohol user=1/ former alcohol user=2/ never alcohol user=3.

12. Other associated conditions (if any):

GIT surgery/ Chr. Diarrhoea/ Chr. Vomitting/Renal disease/ cancer/ pregnancy/others (specify):

13. No of childbirth (in females):

Time of last childbirth:

Duration of Lactation:

12. Presenting Symptoms:

12.1) Limb Weakness: Upper limb/ lower limb/ both. Duration:.....days

12.2) Leg swelling: yes/ no. Duration.....days

Nil=0, Mild=+, moderate=++, severe=+++

12.3) Sensory Impairment (pain, tingling, numbness): yes/ no. Duration: Days.

12.4) anorexia , nausea : yes/ no. Duration: Days.

12.5) Muscle cramp: no/mild/moderate/severe. Duration: Days.

12.6) other symptoms (specify): Duration: Days.

13. Physical Examination:

13.1) Height:, weight:.....Kg, BMI (weight/height²):

13.2) Mid Upper Arm Circumference(MUAC):.....cm

13.3) Anaemia: Absent/ Present.

13.4) muscle power (MMRC Grading):

Upper Limb	Lower Limb
Proximal:	Proximal:
Distal:	Distal:

13.5) deep tendon reflexes: normal =0, Diminished=1, Absent=2

	Biceps	Triceps	Supinator	Knee	Ankle	Planter
Right						
Left						

[figure not shown]
13.6) Squat test: negative=0/ positive=1.

13.7) Sensory Impairment: Normal =0, Diminished=1,Absent=2

	pain	touch	temperature	Position sense	vibration
Upper limb					
Lower limb					

13.8) neuropathic Pain (VAS Score):
nil=0/mild=1/moderate=2/sever=3.

13.8) Pulse :/min

13.9) BP:m m hg

13.10) Resp Rate:/min

13.11) JVP: normal/ Raised

13.12) other :if present,(specify)

14. Investigations:

14.1) CBC:

14.2) Urine R/E:

14.3) Serum creatinine:

14.4 Serum Electrolytes:

14.5) LFT: a) SGPT:

b) SGOT

c) PT:

d) Serum Albumin:

14.6) OGTT a) FBS :

b) 2 hr after 75 gm glucose:

14.7) HbA1C:

14.8) TSH

14.9) serum B12 assay:

14.10) CXR PA view

14.11) ECG

14.12) Echocardiography:

14.13) CSF Study:

14.14) NCS (Nerve conduction study):

15. Therapeutic Response:

Parameters	Assessment Before treatment (A 0) Date:	Assessment After 1 wk (A 1) Date:	Assessment After 6 wk (A 2) Date:	Assessment After 12 wk (A 3) Date:
A) Leg Swelling				
B) Muscle Power (MMRC grading) Upper Limb Lower Limb				
C) Deep Tendon Reflexes Upper Limb Lower Limb				
D) Squat Test				
E) Sensory impairment				
Pain				
touch				
position				
Vibration				
Tingling, Numbness				
Hyperesthesia (VAS score)				
F) Muscle cramp (VAS score)				
H) Overall Neuropathy Limitation Scale (ONLS)	Arm Score..... Leg Score..... Total:	Arm Score..... Leg Score..... Total:	Arm Score..... Leg Score..... Total:	Arm Score..... Leg Score..... Total:

[figure not shown]
Medical Research Council (MRC) Scale for Muscle Power

0	no muscle contraction visible
1	Flicker of contraction but no movement
2	Joint movement when effect of gravity eliminated
3	Movement against gravity but not against examiner's resistance
4	Movement against resistance but weaker than normal
5	Normal power

Muscle tested for Power

Upper limb	Lower limb
Shoulder abduction	Hip flexion
Shoulder adduction	Hip extension
Elbow flexion	Knee flexion
Elbow extension	Knee extension
Supination	Foot dorsiflexion
Pronation	Foot planter flexion
Finger abduction & adduction	Great toe extension
Thumb opposition, abduction & adduction	Great toe flexion

Visual Analogue Scale (VAS) for pain

Neuropathic pain/Hyperesthesia	VAS Score
Nil=0	0
Mild=1	1-3
Moderate=2	4-6
Severe=3	7-10

Overall Neuropathy Limitations Scale (ONLS)

Instructions: The examiner should question and observe the patient in order to determine the answers to the following questions. Note should be made of any other disorder other than peripheral neuropathy which limits function at the foot of the page.

ARM SCALE:

Does the patient have any symptoms in their hands or arms, eg tingling, numbness or weakness? Yes/ No.

(if "no", please go to "legs" section)

Is the patient affected in their ability to: Not affected /Affected but not prevented/
Prevented

1. Wash and brush their hair
2. Turn a key in a lock
3. Use a knife and fork together (or spoon, if knife and fork not used)
4. Do or undo buttons or zips
5. Dress the upper part of their body excluding buttons or zips
6. If all these functions are prevented can the patient make purposeful movements with their hands or arms?

Arm Grade

0= Normal

1= Minor symptoms in one or both arms but not affecting any of the functions listed

2= Disability in one or both arms affecting but not preventing any of the functions listed

3= Disability in one or both arms preventing at least one but not all functions listed

4= Disability in both arms preventing all functions listed but purposeful movement still possible

5= Disability in both arms preventing all purposeful movements

Arm SCORE=

LEG SCALE

Does the patient have difficulty running or climbing stairs?

Does the patient have difficulty with walking?

Does their gait look abnormal?

How do they mobilise for about 10 metres (ie 33 feet)?

Without aid

With one stick or crutch or holding to someone's arm

With two sticks or crutches or one stick or crutch holding onto someone's arm or frame

With a wheelchair

If they use a wheelchair, can they stand and walk 1 metre with the help of one person?

If they cannot walk as above are they able to make some purposeful movements of their legs, eg reposition legs in bed?

Does the patient use **ankle foot orthoses/braces?** (if yes, please circle) **right/left**

Leg grade

0= Walking/climbing stairs/running not affected

1= Walking/climbing stairs/running is affected, but gait does not look abnormal

2= Walks independently but gait looks abnormal

3= Requires unilateral support to walk 10 metres (stick, single crutch, one arm)

4= Requires bilateral support to walk 10 metres (sticks, crutches, crutch and arm, frame)

5= Requires wheelchair to travel 10 metres but able to stand and walk 1 metre with the help of one person

6= Restricted to wheelchair, unable to stand and walk 1 metre with the help of one person, but able to make some purposeful leg movements

7= Restricted to wheelchair or bed most of the day, unable to make any purposeful movements of the legs

Is there any disorder, other than peripheral neuropathy, which affects the above functions: Yes / No

If yes please describe:

Leg SCORE=

TOTAL SCORE= (Arm SCORE) + (Leg SCORE)

Overall Neuropathy Limitation Scale = arm scale (range 0 to 5) + leg scale (range 0 to 7); range: 0 (no disability) to 12 (maximum disability).

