According to World Health Organization (WHO) International Nomenclature of Diseases, Thiamine deficiency (TD) syndrome is a clinical syndrome that arises insidiously as a result of a severe, prolonged deficiency of thiamine in the diet, manifested in the initial stages by anorexia, malaise, and weakness of the legs, frequently with paraesthesia; there may be slight oedema and palpitations. The disorder may persist in this chronic state or may at any time progress to an acute condition characterized either by cardiac involvement with oedema or by peripheral neuropathy; forms intermediate between these two extremes may also occur. It is thought that the basic cause is the inhibition of a series of enzyme-catalysed cleavages of carbon-carbon bonds in which thiamine diphosphate is a coenzyme. Commonly used synonyms are beriberi; Ceylon sickness; occidental beriberi (in part); oriental beriberi (in part); rice disease etc. The disorder (or spectrum of disorders) is classically associated with a diet consisting largely of polished rice (oriental beriberi), but may also arise if highly refined wheat flour forms a major part of the diet, in alcoholics, and in food faddists (occidental beriberi).¹

Thiamin (vitamin B1) is widely distributed in foods of both vegetable and animal origin. It is an essential micronutrient with dual coenzymatic and non-coenzymatic functions. It is involved in carbohydrate and branched-chain amino acid metabolism, as well as in the production of neurotransmitters, myelin, and nucleic acids. There is also evidence that thiamine plays a role in immune and anti-inflammatory processes and gene regulation.²⁻⁵

The human body requirement for thiamine is exclusively dependent on regular dietary intake, as there is no significant mechanism for endogenous production of thiamine or for prolonged storage of thiamine in the human body. It is estimated that the body can store thiamine for 2–3 weeks. Staple diets that are deficient in thiamine would result in low body thiamine levels, which may be subclinical or may manifest as a thiamine-deficiency syndrome. Thiamine deficiency is classically associated with diets consisting mainly of

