milled white cereals, particularly polished rice and highly refined wheat flour. Milling significantly reduces the thiamine content of cereals: the thiamine content of highly milled white rice is 0.08 mg/100 g compared with 0.33 mg in unmilled brown rice. Rice washing and cooking methods may result in additional losses of up to 45–60% of thiamine. Rice is the most important food source in our country. The combination of limited body storage and a high turnover rate (half-life <10 days) results in potential depletion of thiamine stores within 2 weeks if it is not continuously replaced. In addition, thiamine's hydrosolubility, coupled with its renal clearance profile, contributes to a propensity to thiamine deficiency (TD) throughout life.^{1,6}

It principally affects precarious communities where children and adults are most vulnerable and where dietary habits rely on refined processed cereals or tubers (e.g., rice, wheat, cassava), notably in Southeast Asia and Africa. TD can result from various mechanisms that are not mutually exclusive. The most frequent mechanisms are insufficiency of dietary thiamine (enteral–parenteral supply) and poor intestinal absorptive capacity during malnutrition, tropical enteropathy, or secondary to surgical resection of large portions of the gastrointestinal tract. A relative inadequacy of thiamine content to caloric ratio (high carbohydrate diets) is also common. It is this thiamine–calorie imbalance that is responsible for TD in heavy drinkers of sweet drinks and contributes to the onset of TD when dextrose-based fluids are administered without thiamine supplementation in critically ill patients. Poor thiamine intake may be due to losses from food secondary to pre-cooking and food processing (e.g., repetitive rice washing), a restrictive diet due to cultural habits and ingestion of antithiamine factors (tea leaves, betel nuts, and coffee) or thiaminases (e.g., fermented raw fish, mycotoxins, stored food, and larvae) that break down and, thus, inactivate thiamine. Excessive loss of thiamine from the body, such as renal (loop diuretics, osmotic diabetic diuresis) or digestive losses (chronic diarrhea, hyperemesis), can also precipitate TD. At cellular level, two main mechanisms contribute to TD – impaired uptake or increased demand. Impaired cellular uptake of thiamine can be due to defects in thiamine transporters or specific enzymes (mutation, hypomagnesemia, drug-induced interaction), or reduced

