- What is the clinic-epidemiological profile of adult patients with suspected dry beriberi ?
- How do they response to therapeutic thiamine challenge?

3. Objectives:

3.1 General objective:

- To evaluate the efficacy of Thiamine in patients with suspected / possible dry beriberi

3.2 Specific objectives:

1. To describe the socio-demographic profile of patients
2. To categorize the patients according to their presenting symptoms and signs.
3. To assess and compare pre and post treatment neurological features

4. Rationale:

A vast population of southern area of Chittagong division of Bangladesh (Satkania, Bashkhaki, Cox'sbazar, Teknaf, Moheshkhali, Saint martin) are at risk of developing thiamine deficiency syndrome due to their dietary habit and low socio-economic condition. In our day to day clinical practice we have encountered many of them with neurological complaints mimicking thiamine deficiency (TD). However, TD has a large clinical spectrum, and as such it is frequently misdiagnosed, sometimes with fatal consequences or permanent neurological sequelae. TD can be investigated using plasma, erythrocytes, whole blood ThPP levels, and urinary excretion of thiamine before and after exogenous thiamine administration. But none of these investigations allow immediate diagnosis of TD in life-threatening conditions and they are rarely available in resource-limited settings. So, the diagnosis of TD in such contexts is a real challenge and a high level of clinical suspicion should be demonstrated in such situations. Early treatment with thiamine has the potential to rapidly reverse clinical signs and minimize sequelae, before the onset of fixed lesions. The lack of diagnostic capacity in our settings justifies the use of a therapeutic thiamine challenge in cases with high clinical suspicion. It is an effective, inexpensive, and easy to administer medication.

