This issue of dry beriberi has got less attention and in our extensive literature search we have failed to identify any document related to dry beriberi in this part of Bangladesh. So, it is rational to design a prospective study to determine the clinical pattern of patients with suspected dry beriberi and their outcome to thiamine therapeutic challenge in our setting. Our study result is likely to sensitize the health professionals of this region about this neglected health issue by increasing awareness of the clinical spectrum of TD. Moreover, study may provide the impetus for fashioning national policies on the diagnosis, treatment and prevention of thiamine deficiency disorders in our country.

5. Metarials and methods:

5.1 Type of study: Quasi-experimental study, self –controlled clinical trial (pretest – posttest design)

5.2. Period of study: One year.

5.3. Place of study: Department of Neurology, Department of Medicine of Chittagong Medical College Hospital.

5.4. Study population: All the patients admitted in the above mentioned ward of CMCH with clinical diagnosis of suspected dry beriberi.

5.5. Sampling technique: Required number of patients will be selected purposively as per set criteria

5.6. Eligibility criteria:

Inclusion criteria:

1. Any person admitted to CMCH as a Suspected/Possible dry-beriberi.

Risk factors + at least 2 of the following signs:

Risk factors include Imbalanced diet (diet poor in thiamine/rich in carbohydrate or anti-thiamine factors), malnutrition, alcoholism, GIT surgery, chronic diarrhoea, chronic vomiting, pregnancy or history of recent delivery, chronic. diuretics use, renal dialysis, total parenteral nutrition.

- a) Muscle weakness of upper and or lower limb (less than grade 5 power in MRC scale)
- b) Positive sensory symptoms (burning, tingling or pain)
- c) Objective sensory deficit (pain, touch, position, vibration sense)
- d) Absent or reduced deep tendon reflexes
- e) Positive squat test (unable to rise after squatting without help)
- f) Leg swelling

2. Age 18 years and above

Exclusion criteria:

1. Patients with isolated cardiac/wet beriberi
2. Patient with known causes of peripheral neuropathy such as Diabetic, hereditary, Demyelinating (GBS, CIDP), metabolic (hepatic/renal impairment), drugs (e.g. INH, Ethambutol, Phenytoin, Metronidazole, Dapsone etc.) Toxin (As ,OPC, Pb ,Hg except alcohol) etc.
3. Patients refuse to participate

5.7. Sample size:

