All the data will be checked and edited after collection. Continuous data will be reported as the means \pm SD or median and itraquartile range. Qualitative or categorical data will be described as frequencies and proportions. Proportions will be compared using chi-square or Fisher's exact test whichever will be applicable. To determine whether any of the difference between pretreatment and post treatment values were statistically significant or not, either Friedman's test or Cochran's Q test were used. Former test compares the quantitative variables and non-dichotomous qualitative variables and the later test compares the dichotomous qualitative/categorical variables. Statistical significance will be defined as $P < 0.05$ and confidence interval will be set at 95% level. SPSS (Statistical Package for Social Science) for Windows version 23 software will be used for the analyses.

5.11. Variables under study:

Primary Outcome Variable:

1. Treatment response measured by Overall Neuropathy Limitation Scale (ONLS) score before and after treatment.

Secondary Outcome Variables:

1. Comparison and Assessment of clinical features at presentation and after treatment: leg swelling, muscle cramp, muscle power (MRC grading), deep tendon reflexes, sensory impairments (tingling /burning /pain/ touch/ position /vibration), squat test.

5.12 Operational definition:

Risk factors: Imbalanced diet (diet poor in thiamine/rich in anti-thiamine factors), malnutrition, alcoholism, GIT surgery, chronic diarrhea, chronic vomiting ,pregnancy, diuretics, renal dialysis, total parenteral nutrition.

Anti-Thiamine factors: Raw or fermented fish,shell fish,ferns, Tea, coffee, betel nuts

Possible/suspected dry beriberi: Risk factors + at least 2 of the following signs:

- a) Muscle weakness of upper and or lower limb (less than grade 5 power in MRC scale)
- b) Positive sensory symptoms (burning, tingling or pain)
- c) Objective sensory deficit (pain, touch, position, vibration sense)
- d) Absent or reduced deep tendon reflexes
- e) Positive squat test (unable to rise after squatting without help)
- f) Leg swelling

Probable dry beriberi: Above symptoms recovered after thiamine treatment.

Socio-economic status: It will be measured as per Modified Kuppuswamy Socio-economic scale (Appendix-A) and grouped into five categories :Upper class, Upper middle class, Lower middle class, Upper lower class and Lower class.

5.14. Utilization of results:

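### The case record form codes only polished rice, omits three defined anti-thiamine foods and uses one religion code twice, so the descriptive profile can be distorted

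*Combined protocol and SAP*

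**What the plan says.** The first research question in section 2 is "What is the clinic-epidemiological profile of adult patients with suspected dry beriberi", and specific objective 1 in section 3.2 is the socio-demographic profile. Three items in Part G, Case Record Form, supply part of that description.

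- **Item 10a (rice):** "Rice eaten: Polished un-boiled=1/polished boiled=2". There is no other code.
- **Item 10f (anti-thiamine foods):** "Anti-thiamine food intake: Betel nut/ tea/ fermented fish/shell fish", followed by a single line for minutes after the meal and times per day. Section 5.12 defines the anti-thiamine factors as "Raw or fermented fish,shell fish,ferns, Tea, coffee, betel nuts".
- **Item 4 (religion):** "Muslim=1/ Hindu=2/Buddist=3 / Christian=3".

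The Introduction describes thiamine deficiency as "classically associated with a diet consisting largely of polished rice" and gives the contrast in figures: "the thiamine content of highly milled white rice is 0.08 mg/100 g compared with 0.33 mg in unmilled brown rice". The entry criteria in section 5.6 require a risk factor plus at least two signs. The dietary risk factor begins "Risk factors include Imbalanced diet (diet poor in thiamine/rich in carbohydrate or anti-thiamine factors"; it does not name polished rice.

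Item 10e is a free-text grid for the contents of five meals and snacks. The time schedule (5.15) has a row for piloting and finalising the form.

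**The concern.** A coded item can describe a population only if its answers can differ on the feature of interest. Item 10a can separate boiled from un-boiled rice but not polished from unpolished. A table built from it would show polished rice for every coded patient whatever they ate.

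Items 10b and 10c record washing and discarded cooking water, which are later steps in the account of thiamine loss that the Introduction gives. Milling, the first step, is the one that the form cannot record.

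Item 10f raises a second issue. A diet rich in anti-thiamine factors is a qualifying risk factor for entry, so a patient who qualifies through coffee, ferns or raw fish has no tick option that documents why. A blank in 10f could mean none, an unlisted food or not asked. One timing and frequency line cannot properly describe a patient who takes both tea and betel nut.

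At stake is the accuracy of the descriptive profile.

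**Working it through.** The plan states no figure on this point, so there is none to reproduce. The check is a count of codes, followed by an illustration of scale.

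**Step 1. Codes against definitions**

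| Item | Needed, and source | On the form | Lost |
|---|---|---|---|
| 10a rice | Polished and unpolished (Introduction) | 2 codes, both polished | Unpolished, mixed, other staple or no rice |
| 10f foods | 7 (section 5.12): raw fish, fermented fish, shellfish, ferns, tea, coffee, betel nut | 4 | 7 − 4 = 3: raw fish, ferns, coffee; also no answer for none |
| 4 religion | 4 categories printed in the item | 3 distinct codes | Buddhist against Christian |

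For 10a, the coded polished share is (code 1 + code 2) / (code 1 + code 2) = 100% for any data. A patient who eats no polished rice is either given a polished code or left blank, and the share among non-blank answers is 100% both ways.

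**Step 2. Scale for the rice item**

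Inputs: n = 55 (section 5.7) and a true polished-rice share t, which the documents do not give. The values of t below are assumptions, and patients are treated as independent.

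- Expected patients with no valid code: n(1 − t)
- Overstatement of the share: 100(1 − t) percentage points
- Chance that no patient is affected: t^n

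| Assumed t | n(1 − t) | Overstatement | t^55 |
|---|---|---|---|
| 100% | 0 | 0 points | 100% |
| 95% | 55 × 0.05 = 2.75 | 5 points | 6.0% |
| 90% | 55 × 0.10 = 5.5 | 10 points | 0.3% |
| 80% | 55 × 0.20 = 11 | 20 points | below 0.001% |

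**Step 3. One assumed case as it would be reported**

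Suppose 50 of 55 patients truly eat polished rice: 50/55 = 90.9% (exact 95% CI 80.0% to 97.0%). If the other five are given a polished code, the table shows 55/55 = 100%, with lower exact limit 0.025^(1/55) = 93.5%. That interval reflects sampling error only and says nothing about the missing category. If the five are left blank, the table shows 50/50 = 100% with five missing.

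**Step 4. What other fields recover**

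Item 10e can hold wheat, a mixed diet, coffee, ferns or raw fish if the interviewer writes them down. It does not ask about milling, so an entry of rice does not settle rice type. For religion, the word may still be legible if it was circled on paper; the two groups merge once code 3 is entered.

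**Step 5. What does not depend on these items**

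The primary outcome (ONLS) and the clinical secondary outcomes in section 5.11 do not use them. Nor do the sample size in 5.7 and the before-after tests in 5.10.

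**The case against.** The strongest reply is that nothing may actually go wrong. The Introduction calls rice the country's most important food source. If every enrolled patient eats polished rice, a recorded 100% is correct. Item 10a asks about rice, not the staple, so it can be left blank; free text catches part of the rest; the religion code is a numbering slip; and the form is still to be piloted and finalised. Section 5.10 names no dietary analysis.

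Most of this stands and sets the size of the point. Two parts do not remove it. Even if 100% is true, the form could not show it, because it would give the same result otherwise. And the finalisation step is an opportunity to correct the items, with no sign in the documents that they will be corrected.

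A reader might infer more than the documents support:

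- **That the profile will come out wrong.** This needs patients outside the listed codes, and no share is given.
- **That polished rice is the study's formal main exposure.** That is an inference from the Introduction. The risk factor in 5.6 and 5.12 is an imbalanced diet, and the end of the Introduction and the Rationale refer only to dietary habit.
- **That the flawed table would mislead about dietary cause, and better codes would cure this.** How readers would take the table is speculation. A single-arm study whose entry criteria include imbalanced diet cannot show cause with any coding.

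**Conclusion.** All three defects are on the face of the form. Item 10a cannot tell polished from unpolished rice, and its coded polished share is 100% by construction. Item 10f covers four of the seven foods in section 5.12, has no answer for none, and has one timing and frequency line for all foods. Item 4 uses code 3 twice.

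The consequence is conditional. The overstatement of the polished share is zero if all patients eat polished rice, and 5, 10 or 20 points if 95%, 90% or 80% do. Those shares are assumptions, and they describe coded answers before any use of the free text. For 10f and religion the documents give no basis for a size.

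The effect is confined to the description of patients under research question 1 and specific objective 1. This is a minor data-capture correction; it is worth making because rice type, if not asked at enrolment, may not be recoverable later.

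**What to change.** At the form finalisation step already in the time schedule:

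1. **Item 10a:** keep the two polished codes and add unpolished or brown rice, mixed, and other staple or no rice.
2. **Item 10f:** list all seven section 5.12 foods, each with its own yes/no and its own timing and frequency. A full set of no answers then records none and is distinct from missing.
3. **Item 4:** code Christian as 4.

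The cost is an edit before printing and a few more tick boxes per patient. No change to the analysis, outcomes or sample size is needed. If any forms have already been completed, recover what is possible from the free-text meals and the circled words, and report rice type for those patients as not determined where milling was not recorded.

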This study result will be helpful to formulate a guideline for the management of suspected case of dry beriberi in our setting and improve the outcome of beriberi by reducing over or under treatment. Further research on such procedure can be designed by utilizing the results of this study.

6. Facilities:

Administrative setup and resource persons are available in the study site.

[figure not shown]
7. Approval of the head of the research cell and ERC:

Under consideration.

8. Clarification of the ethical issue:

1. Voluntary consent will be taken from each patient to be enrolled for the forthcoming study. patient's legal guardian will be approached where required.
2. All measures will be taken to preserve patients' anonymity and privacy. To do such, a separate case record form (CRF) will be utilized for every patient issuing a different identity code and only principal investigator will have access to patients' data. To be more, personal information of any of them will not be handed over any third party without their consent.
3. Evaluation of each research participant will be done thoroughly. Required investigations including radio-imaging and biochemical tests will be done in the CMCH if facilities available.
4. They will be treated as per treatment guideline for the disease of research interest. Importantly, no financial support will be provided to any research participant for being a subject in the research work.
5. All patients' will be informed about the nature and purpose of the study. They will get informed that their participation in the coming study research will not only benefit them but also the whole community as well.

5.13. Flow Chart of Study Design:

5.15 Time schedule:

	item	July to August 2018	September to October 2018	November 2018 to April 2019	May 2018	June 2019
1	Literature search & protocol writing					
2	Piloting & CRF(Case record form) Finalization					
3	Data collection					
4	Data entry					
5	Data analysis					
6	Report writing					
7	submission					

References:

1. WHO & UNHCR. 1999. Thiamine deficiency and its prevention and control in major emergencies. WHO/NHD/99. 13.

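### The primary ONLS is scored by an unmasked examiner with earlier scores in view, partly from answers of patients told they will benefit; two near-free edits would reduce the risk of bias

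*Combined protocol and SAP*

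**What the plan says.** - **Outcome.** Section 5.11 gives the primary outcome as "Treatment response measured by Overall Neuropathy Limitation Scale (ONLS) score before and after treatment". The form's closing note runs the total from 0 (no disability) to 12 (maximum disability), so a lower score is better.
- **Design and masking.** Section 5.1 describes a self-controlled, before-and-after study, and the CRF title (Part G) calls it "An Open Labeled Hospital Based Study". No section names a masked, independent or fixed assessor.
- **Who scores.** The ONLS form instructs: "The examiner should question and observe the patient in order to determine the answers to the following questions". The examiner decides the grade; the patient supplies some of the information.
- **Where it is recorded.** CRF item "15. Therapeutic Response" is one table whose columns run from "Assessment Before treatment (A 0) Date" to "Assessment After 12 wk (A 3) Date", with weeks 1 and 6 between them. Its ONLS row takes an arm, leg and total score for each visit. Nothing tells the examiner to cover the earlier columns.
- **What patients hear.** Section 8, item 5 says they will be told that taking part "will not only benefit them but also the whole community as well".
- **What the investigators expect.** The Introduction reports that most such patients respond in the investigators' experience, and Section 5.7 puts the proportion at 80%.

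**The concern.** Whether thiamine helps these patients is the general objective (Section 3.1). The plan measures this with a scale that needs judgement, applied by someone who knows the treatment and can see the previous scores, to patients already told to expect benefit.

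In a trial with a concurrent control, some of a shared rating shift would cancel between arms. Here there is nothing to cancel against: any systematic lowering of follow-up scores goes straight into the before-and-after difference that will be reported as efficacy. Two of the contributing features, the sheet layout and the benefit statement, can be changed without altering the design.

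**Working it through.** **1. Where judgement enters the score.** From the printed grade definitions:

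- Arm grades 0 to 3 turn on whether symptoms are present and whether listed tasks are unaffected, affected or prevented. Much of this comes from questioning.
- Leg grade 0 against 1 turns on difficulty with walking, stairs or running. Grade 1 against 2 turns on whether the gait looks abnormal to the examiner.
- Leg grades 3 and above rest mainly on the support used over 10 metres, which leaves less discretion.

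The room for a one-point shift is therefore mostly at the milder end of both scales.

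**2. Direction of each influence.**

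| Feature | Where | Likely direction |
|---|---|---|
| Examiner and patient know treatment was given | CRF title, Section 5.1 | Lower follow-up ONLS (apparent improvement) |
| Patients told they will benefit | Section 8, item 5 | Lower follow-up ONLS |
| Earlier scores in view | CRF item 15 | Uncertain: scores may be held near baseline, or moved away from it in the expected direction |

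**3. How large a shift would matter.** The plan has no figure for rating error or bias, so there is none to reproduce. What follows is illustration only.

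Inputs from the plan: four visits; P < 0.05 and Friedman's test for quantitative and non-dichotomous variables (Section 5.10); 42 or 55 patients (Section 5.7).

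Assumptions, not in the plan: no true change; true ONLS equally likely to be any whole number from 2 to 8; a random error of one point, up or down with equal chance, in 20% or 40% of ratings; and a fraction b of post-baseline ratings scored one point too low, either independently by visit or in the same patients throughout. There were 2,000 simulated trials per setting.

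Observed rating = true score + random error − 1 (with probability b, post-baseline visits only), kept within 0 to 12. The average shift is b × 1 point, so b = 20% is 0.2 points on the 12-point scale.

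| b | Share of trials with P < 0.05 (range over settings) |
|---|---|
| 0 | 0.046–0.057 |
| 5% | 0.053–0.077 |
| 10% | 0.07–0.16 |
| 20% | 0.18–0.49 |
| 30% | 0.39–0.83 |

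The b = 0 row recovers the nominal 5%; simulation error there is about √(0.05 × 0.95 / 2000) = 0.005. The model contains only a favourable shift. It does not represent anchoring, and it does not show how much of the shift the proposed edits would remove.

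**4. Cost of extra sheets.** With 55 patients and four visits, 55 × 4 = 220 item forms are needed, or 55 × 3 = 165 beyond one per patient. Part E lists 10,000 taka for printing and 5,000 for photocopying, and no personnel cost. It gives no price per page.

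**The case against.** The strongest reply is that the gain is small. After both edits the examiner and the patient still know treatment was given, and there is still no control arm. Many leg grades rest on visible aids, and the instrument already defines its grades by function. Only expectation clearly favours thiamine; an examiner anchored on baseline could understate change. At a 5% mis-scoring rate the illustration hardly departs from nominal. All of this stands, and it limits the point to a cheap improvement.

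Four stronger readings are tempting, and the documents do not support them:

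- *Patients rate the primary outcome.* They do not; the scoring instruction gives that to the examiner.
- *The outcome is biased in favour of thiamine.* The documents show conditions for bias, not its occurrence or size, and the effect of visible earlier scores has no certain direction.
- *The item form is completed only once per patient.* It is printed once, as a blank form normally is. The plan does not say whether it is repeated at each visit. It shows only that item 15 has room for arm, leg and total scores and not for item answers.
- *The consent form promises benefit.* The consent pages are not in the review copy. Section 8, item 5 states what patients will be told, while Section 5.9 also promises a full explanation of outcome, complications and purpose.

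**Conclusion.** The point holds as a risk that the plan leaves open, of minor severity. The documents establish unmasked scoring by an examiner, earlier scores on the same table, a statement of benefit to patients, a single group, and no stated mitigation.

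The size is unknown. The simulated percentages depend on the assumed error model and should not be quoted as this trial's false-positive rate. They show that a favourable shift averaging 0.2 points could matter, and that one averaging 0.05 points would hardly show.

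A significant before-and-after change would still not isolate the effect of thiamine even with perfect rating, because natural recovery and regression to the mean remain.

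**What to change.** 1. **CRF.** Add a separate, dated ONLS item sheet for each of the four visits. State that it is completed without sight of earlier sheets or of item 15, that arm and leg grades are taken from the item answers recorded on it, and that scores are copied into item 15 afterwards. This also leaves an auditable record of the primary outcome.
2. **Section 8, item 5, and the patient information if it says the same.** Replace the benefit statement with a neutral one: participants may or may not benefit.
3. **Reporting.** Acknowledge unmasked rating and the lack of a control group as limitations of the ONLS result.

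The cost is a few more printed pages per patient, a short instruction and one changed sentence. No extra staff are needed. An independent assessor would go further, but the plan has no personnel budget, so that is not proposed as a free change.
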